7.4 Restitution of the programs

All programs (including Macros and SAS® analysis datasets) producing the tables, listings and statistical output along with associated logs should be given to the sponsor when the tables, listings, figures and statistical analysis has been finalised.

8 STATISTICAL APPENDICES

APPENDIX (Derived data)

The following derived data will be calculated and included in the listings:

(1) **Enrollment duration**

Enrollment duration (days) = date of inclusion of the last patient – date of inclusion of the first patient

(2) **Time between first medical events related to GCA and diagnosis**

For prevalent patients (not newly diagnosed):

Time between first medical events related to GCA and diagnosis (months) = date of diagnosis – date of first medical events related to GCA

For incident patient (newly diagnosed):

Time between first medical events related to GCA and diagnosis (months) = date of diagnosis (in MM/YY format) – date of first medical events related to GCA

The date of diagnosis which is in format (DD/MM/YYYY) will be transformed into (MM/YYYY)

(3) **Time between diagnosis and inclusion**

For prevalent patients:

Time between diagnosis and inclusion (months) = (date of inclusion – date of diagnosis)/30.4375

If the date of diagnosis in format (DD/MM/YYYY) is not completed, the diagnosis date in format (MM/YYYY) will be used and the inclusion date will be transformed into (MM/YYYY).

For incident patients:

Time between diagnosis and inclusion (months) = (date of inclusion – date of diagnosis)/30.4375

The date of diagnosis in format (DD/MM/YYYY) will be used.

(4) **Duration of treatment taken**

Duration of treatment taken (months) = End date – start date +1

if ongoing treatment at inclusion:

Duration of treatment taken = Date of inclusion – start date +1

For this calculation, the date of inclusion which is in format (DD/MM/YYYY) will be transformed into (MM/YYYY) as the start date of treatment.

(5) **Time between first relapse and diagnosis**

Time between first relapse and diagnosis (months) = date of first relapse after diagnosis – date of diagnosis.

For this calculation, the date of diagnosis (for incident patient) which is in format (DD/MM/YYYY) will be transformed into (MM/YYYY) as the date of relapse.

(6) Mean time between 2 consecutive relapses

Time between 2 consecutive relapses (months) = [date of relapse (i+1) – date of relapse (i)]/(Total number of relapses per patient-1)

(7) Time between first kinetic and diagnosis

Time between first kinetic and diagnosis (months) = date of initiation of first kinetic – date of diagnosis

For this calculation, the date of diagnosis (for incident patients) which is in format (DD/MM/YYYY) will be transformed in to (MM/YYYY) as the date of kinetic.

(8) Mean time between 2 consecutive kinetics

Mean time between 2 consecutive kinetics (months) = [date of kinetic (i+1) – date of kinetic (i)]/Total number of kinetics per patient

(9) Duration of kinetic

Duration of kinetic (months) = Stop date of kinetic – Initiation date of kinetic +1

if ongoing kinetic at inclusion:

Duration of kinetic (months) = Date of inclusion – Initiation date of kinetic +1

For this calculation, the date of inclusion which is in format (DD/MM/YYYY) will be transformed in to (MM/YYYY) as the Initiation date of kinetic.

(10) Total cumulative GCs dose since diagnosis

Total cumulative GCs dose (mg) = Σ Cumulative dose according to the investigator (excluding IV bolus) taken in each kinetic since diagnosis

(11) Age

Age (years) = (date of inclusion – birth date)/365.25 and truncated to the lowest whole integer.

(12) BMI

BMI (kg/m²) = Current weight (kg)/ [Height (cm)/100]² and rounded to the nearest decimal.

(13) Number of years since the medical school graduation

Number of years since graduation (years) = Year of inclusion date – year of medical school graduation

(14) **FACIT-Fatigue score**

The FACIT-Fatigue is an instrument that measures overall fatigue and its effects on the general functioning and daily activities through 13 questions.

The FACIT-Fatigue is a patient-reported rating scale of 13 items rated from 0 (not at all) to 4 (very much), including 11 negative items with a reversed score for calculating the score:

N° item	Reversed item?	Not at all	A little bit	Some what	Quite a bit	Very much
1	Yes	4	3	2	1	0
2	Yes	4	3	2	1	0
3	Yes	4	3	2	1	0
4	Yes	4	3	2	1	0
5	Yes	4	3	2	1	0
6	Yes	4	3	2	1	0
7	No	0	1	2	3	4
8	No	0	1	2	3	4
9	Yes	4	3	2	1	0
10	Yes	4	3	2	1	0
11	Yes	4	3	2	1	0
12	Yes	4	3	2	1	0
13	Yes	4	3	2	1	0

The total score of FACIT-Fatigue varies from 0 to 52 and is calculated with respect to the items answered:

$$[(\Sigma \text{Answered items scores}) / \text{number of items answered}] * 13$$

This calculation method allows for the management of missing data and remains acceptable if more than 50% of the items (i.e. at least 7 items) have been answered¹.

A score of less than 30 indicates severe fatigue. The higher the score, the better the quality of life is.

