5.2.2 Missing or incomplete dates

For all dates

- if only the day part is missing, it will be replaced by 15 (only when date is in format DD/MM/YYYY)
- if only the month part is missing and it is a former date (for example the date of diagnosis), it will be replaced by June
- if the day and month parts are missing and it is a former date (for example the date of diagnosis), day will be replaced by 1 and month will be replaced by July

- if the year part is missing or the complete date is missing, no replacement will be performed and calculation will be considered as missing

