5.2.3 Outliers

Any outlier identified prior to database lock which is impossible/implausible will be excluded from the analysis. A search of outliers should be performed before the database lock and actions with the sponsor should be defined (during data review meeting).

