5.4 Analyses of primary objectives

To describe medical practices in patients with GCA, the following endpoints will be described on the analysis population:

- Patient journey
 - Proportion of each medical speciality of the physician who has referred the patient (General practitioner/ Ophthalmologist / Neurologist/ Emergency/ Internist/ Rheumatologist/Other)
A listing of Other will be presented.
 - Proportion of each medical speciality of physicians who follows the patient for his/her GCA (Internist/ Rheumatologist/Other)
A listing of Other will be presented.
 - Time between the first medical events related to GCA and diagnosis (months) (type of diagnosis) described as quantitative variable and as qualitative variable. (Early diagnosis (if < 1month) / Diagnosis in the standard time (if between 1 month and 3 months) / Late diagnosis (if > 3 months)) ([APPENDIX](#))
 - Proportion of patients considered with late diagnosis by the physician who referred the patient (Yes/No)
 - Proportion of patient who encountered each medical speciality since the first events related to GCA (Horton).
 - Number of type of medical specialities encountered by the patient since the first events related to GCA (Horton). If a patient encountered a medical speciality more than one time, this speciality will be counted only once.

The first 2 endpoints will be described overall and by time between first medical events and diagnosis (Early diagnosis/ diagnosis in the standard time/ late diagnosis)

The 1st,3rd and 4th endpoints will be described overall and by type of physicians who follows the patient.

- Diagnostic elements used for GCA diagnosis
 - Proportion of each diagnostic element
 - Signs/symptoms (Yes/No/ intermediate)
 - Erythrocyte Sedimentation Rate (ESR) done (Yes/ No)

- If yes, contributing to diagnosis (Yes/ No/ intermediate)
- C-Reactive protein (CRP) done (Yes/ No)
 - If yes, contributing to diagnosis (Yes/ No/ intermediate)
- Biopsy of the temporal artery (TAB) done (Yes/ No)
 - If yes, contributing to diagnosis (Yes/ No/ intermediate)
- High resolution color Doppler ultrasound of the temporal arteries done (Yes/ No)
 - If yes, contributing to diagnosis (Yes/ No/ intermediate)
- MRI scanner of the temporal arteries done (Yes/ No)
 - If yes, contributing to diagnosis (Yes/ No/ intermediate)
- 18FDG PET positron emission tomography done (Yes/ No)
 - If yes, contributing to diagnosis (Yes/ No/ intermediate)
- Aortic angiography by CT (angio-CT) done (Yes/ No)

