7.3 Validation of programs

Validations will be done according to the procedure of the CRO ITEC Services.

The program reviewer is responsible for reviewing each project program and output provided to the sponsor. Program logs are reviewed for logical, syntax and fatal errors. The review in SAS® includes, but is not limited to, all ERRORS, WARNINGS, BY-VALUE merge messages, NOTES, and UNINITIALIZED variables. Program logs are also reviewed for accurate and consistent variable and observation counts following each procedure and data step.

The reviewing statistician is responsible for checking and reviewing the work produced using whatever method he/she feels is appropriate (e.g., SAS® code review, hand calculation, etc.) to reassure of the quality of the output.

Outputs are reviewed for typographical errors, misspellings and nonsensical values or results and to check the consistency with the statistical and analysis plan. Outputs are cross-checked against each other for accuracy and consistency. For statistical tables, listings, appendix listings, and figures, this procedure includes comparison of subject group numbers, counts of subjects at each observation point, and consistency of results for variables between outputs.

Findings of the quality control reviews are communicated to the party responsible for making necessary changes. The programs will be retested after modifications.

After final review, and when no further changes are required to produce the deliverable, the program reviewer and the statistician in charge of the study need to complete and sign a validation checklist, to indicate that they have successfully performed all of their responsibilities.

Copies of the internal quality control forms produced for the validation process and the sign-off forms will be provided to the sponsor to support the validation if asked.

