9.2 Analyses of primary objectives

Table 2 - Efficacy analysis – Patient journey – Analysis population (N=XX)

Parameter	Statistics	Total (N=XX)
Physician who referred the patient		
General practitioner	n(%)	
Ophthalmologist	n(%)	
Neurologist	n(%)	
Emergency	n(%)	
Internist	n(%)	
Rheumatologist	n(%)	
Other	n(%)	
	Filled, n(%)	
	Missing, n(%)	
Physician encountered by the patient since the first events related to GCA*†		
General practitioner	n(%)	
Ophthalmologist	n(%)	
Neurologist	n(%)	
Emergency	n(%)	
Internist	n(%)	
Rheumatologist	n(%)	
Other	n(%)	
Number of type medical specialities encountered by the patient since the first events related to GCA†	Mean SD Median [Q1 ; Q3] [Min ; Max] Filled, n(%) Missing, n(%)	
Physician who follows the patient for his/her GCA		
Internist	n(%)	
Rheumatologist	n(%)	
Other	n(%)	
	Filled, n(%)	
	Missing, n(%)	
Time between the first medical events related to GCA and diagnosis*		
Early diagnosis	n(%)	
Diagnosis in the standard time	n(%)	
Late diagnosis	n(%)	
	Filled, n(%)	
	Missing, n(%)	
Patients considered with late diagnosis by the physician who referred the patient		
No	n(%)	
Yes	n(%)	
	Filled, n(%)	
	Missing, n(%)	

* Multiple answers possible

† If a patient encountered a medical speciality more than one time, this speciality will be counted only once

The percentages are calculated compared to filled data

Early diagnosis if time < 1 month

Diagnosis in the standard time if time between 1 and 3 months

Late diagnosis if time > 3 months

STUDY : CHUGAI-ARTEMIS - Edition date: DDMMYY

Pgm : EFFICACYJOURN.SAS

Listing 1 : Other physician who follow patient (N= XX)

Physician ID	Gender	Specialty	Year of medical school graduation	Number of GCA case personally treated within the last year	Main activity	Location

STUDY : CHUGAI-ARTEMIS - Edition date: DDMMYY
Pgm : EFFICACYJOURN.SAS

Table 3 - Efficacy analysis – Physicians who referred and follow the patients by time between first medical event related to GCA and diagnosis* – Analysis population (N=XX)

Parameter	Statistics	Early diagnosis (N=XX)	Diagnosis in standard time (N=XX)	Late diagnosis (N=XX)
Physician who referred the patient				
General practitioner	n(%)			
Ophthalmologist	n(%)			
Neurologist	n(%)			
Emergency	n(%)			
Internist	n(%)			
Rheumatologist	n(%)			
Other	n(%)			
	Filled, n(%)			
	Missing, n(%)			
Physician who follows the patient for his/her GCA				
Internist	n(%)			
Rheumatologist	n(%)			
Other	n(%)			
	Filled, n(%)			
	Missing, n(%)			

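### SAP 5.2.2 sets a year-only onset to June, so some delays to diagnosis in a primary endpoint come out negative and are counted as early (minor)

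*SAP*

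**What the plan says.** Protocol 6.1 lists the time from signs and symptoms to diagnosis among the patient-journey primary endpoints. SAP 5.4 has it "described as quantitative variable and as qualitative variable", with early below 1 month, standard from 1 to 3 months and late above 3 months. The early class has no lower limit at zero.

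Protocol 5.3.1 collects onset as month and year. SAP section 8, derived data item (2), defines the delay as diagnosis date minus onset date, in months. For incident patients it adds: "The date of diagnosis which is in format (DD/MM/YYYY) will be transformed into (MM/YYYY"). It does not say how a prevalent patient's full diagnosis date is handled.

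SAP 5.2.2 covers all dates. If only the month is missing in a past date, the rule is "for example the date of diagnosis), it will be replaced by June". If day and month are both missing, "day will be replaced by 1 and month will be replaced by July". The day rule, "if only the day part is missing, it will be replaced by 15 (only when date is in format DD/MM/YYYY"), does not reach month/year fields. Nothing requires an imputed onset to fall on or before the diagnosis.

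The shells of SAP Tables 2 and 4 show "Time between the first medical events related to GCA and diagnosis" in three classes only.

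**The concern.** A fixed mid-year month is a tolerable convention for an interval of several years. Here the cut points are 1 and 3 months, and the imputed month can be wrong by up to half a year. The imputed value can therefore cross both cuts, or fall after the diagnosis it should precede. A negative delay is impossible, yet it satisfies the early criterion as written.

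The three classes are more than a primary result. They also define the subgroups for referring physician, following physician and diagnostic methods (SAP 5.4) and for the GCA characteristics (SAP 5.5.2). A late yes/no version is a candidate factor in both logistic regressions in SAP 5.5.2.

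**Working it through.** The documents give no rate or expected distribution for this endpoint, so there is no figure of the plan's own to reproduce. The check has three steps.

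**1. What the rule does (from the text).** Inputs: onset year known and month set to June (SAP 5.2.2); diagnosis month known; delay = diagnosis month minus onset month, in whole calendar months; classes from SAP 5.4.

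| Diagnosis month | Imputed delay (months) | Class given | Classes possible from the known dates |
|---|---|---|---|
| January, same year | 1 - 6 = -5 | early | early only |
| February to April, same year | -4 to -2 | early | early or standard |
| May, same year | 5 - 6 = -1 | early | early, standard or late |
| June, same year | 0 | early | early, standard or late |
| July to September, same year | 1 to 3 | standard | early, standard or late |
| October to December, same year | 4 to 6 | late | early, standard or late |
| January to March, next year | 7 to 9 | late | standard or late |
| April, next year, or after | 10 or more | late | late only |

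The class is right by necessity only in the first and last rows. There are 1 + 2 + ... + 12 = 78 feasible pairs of onset and diagnosis month within one year. The imputed class equals the true calendar-month class in 6 (January to June) + 9 (July to September) + 21 (October to December) = 36 of them, or 46% with equal weights.

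**2. How often, given a year-only onset (assumed delays).** Assumption: onset day uniform over the year and exponential delays with mean 1, 2 or 4 months. The true class comes from exact days / 30.4375. Results are from simulations of 600,000 to 1,000,000 pairs per setting.

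| Mean delay (months) | 1 | 2 | 4 |
|---|---|---|---|
| Wrong class, onset month known | 28% | 23% | 16% |
| Wrong class, onset set to June | 60% | 58% | 46% |
| Negative delay, onset set to June | 33% | 26% | 18% |
| Of the negatives, not truly early | 27% | 43% | 53% |
| Class determined by the known dates | 4% | 6% | 16% |

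With gamma (shape 2, mean 1-4) or log-normal (median 1-4, sigma 1) delays, the June-imputed error is 40-63%. At a median delay of 6 months it is 30%, with 10% negative.

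**3. Whole sample.** Extra misclassification = share year-only × (wrong with June - wrong with month known). The bracket is 60 - 28 = 32, 58 - 23 = 35 and 46 - 16 = 30 points.
- 1% year-only: 0.01 × 30 to 35 = 0.30 to 0.35 points. Of 300 patients, 3 are year-only, and 18-33% of 3 gives 0.5 to 1 negative delay.
- 5% year-only: 0.05 × 30 to 35 = 1.5 to 1.75 points. Of 300 patients, 15 are year-only, and 18-33% of 15 gives about 3 to 5 negative delays.

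The 1% and 5% are illustrations; neither document gives a rate.

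**The case against.** The best defence is that such records should be few and that several checks exist. The case report form asks for month and year. Protocol 8.1 provides correction requests for missing or erroneous data and a data review meeting before the final analysis, and Protocol 12.6 allows written corrections. SAP 5.2.3 says "Any outlier identified prior to database lock which is impossible/implausible will be excluded from the analysis". SAP 5.1 requires minimum and maximum for quantitative data, and SAP section 8 says derived data go into the listings. SAP 7.3 includes code review, and "Outputs are reviewed for typographical errors, misspellings and nonsensical values or results".

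This stands in part: queries may recover some months, and a negative minimum would show if the text of 5.1 and 5.4 were followed. But these checks are general and none changes the imputation rule. The Table 2 and 4 shells omit the quantitative rows, and none of the 13 listing templates has a column for the interval. In those shells a negative delay would look like one more early patient. Nor would a check for negative values find a record imputed to a plausible but wrong positive delay.

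Three stronger readings are tempting and are not supported.
- *Cutting the diagnosis date to month and year is an error.* Onset has no day, so the cut puts both dates on one scale, and a common calendar-month rule would keep it.
- *The delay has no usable month rule.* Subtracting one month/year date from another, with the result labelled in months, reads naturally as a whole-month count, and the +1 in items (4) and (9) fits that. Item (3) divides by 30.4375, but mainly for full dates. The real gap is a prevalent patient's full date in item (2), which needs only clarification.
- *Imputation makes every year-only class arbitrary.* It does not for a January diagnosis in the onset year or for one from April of the next year.

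The June/July difference between field formats is real, but it matters mainly if both dates are year-only in the same year, which should be rare.

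**Conclusion.** The concern holds for the imputation rule, as a minor point. It is certain from the text that SAP 5.2.2, applied to a year-only onset, gives an impossible negative delay for a January to May diagnosis in that year and counts it as early. It is also certain that the imputed month, not the patient's data, sets the class for diagnoses from February of the onset year to March of the next.

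The percentages are conditional on the assumed short delays and fall if delays are longer. The effect on the overall class distribution is probably small, because month and year are both requested. It could be larger only if year-only onsets were common, for example among patients diagnosed years ago, and the documents do not allow that to be judged.

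**What to change.** 1. In SAP 5.2.2, exclude this interval from June/July imputation. Set the class to missing unless the known dates determine it (for a year-only onset: early if diagnosed in January of that year, late if diagnosed from April of the next year). Never count a negative delay produced by imputation as early.
2. Report how many patients are affected.
3. Add mean, median, minimum and maximum rows to Tables 2 and 4, as SAP 5.4 already plans.
4. As a clarification, state in section 8, item (2), that the delay is the whole calendar-month difference for incident and prevalent patients alike, including prevalent patients with a full diagnosis date. Label the classes 0, 1-3 and 4 or more calendar months.

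Cost: a few lines of SAP text and rows in two table shells, with no new data. The downside is that most year-only onset records become missing for this class: 84-96% of them under the assumed means of 1 to 4 months (100% minus the determined shares of 16% and 4%). Settle it before database lock, so that the rule cannot depend on the result.

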- Proportion of patients with at least one general sign at diagnosis and the proportion of each sign (fever $>$ 38°C with no other etiology than GCA, weight loss and its value (%), alteration of the general condition)

For the value of ESR and CRP at diagnosis, only value measured in the previous month, the current month and the month following the date of diagnosis will be considered. For values at inclusion, only measures done within 6 month before the date of inclusion will be considered.

A listing of other initial characteristics related to GCA at diagnosis will be presented.

- Clinical form:
 - Proportion of patients with at least one relapse
 - In patient with at least one relapse:
 - Number of relapses per patient
 - Time between first relapse and diagnosis (months) ([APPENDIX](#))
 - Mean time between 2 consecutive relapses (months) ([APPENDIX](#))
 - The following information will be summarized by relapse:
 - Proportion of used criteria to assess relapse (Clinical/ Biological/ Imagery/ Other)
 - Proportion of patients using GCs just before the relapse
 - GCs dose at relapse diagnosis (mg/day)
 - Proportion of relapses of patients with Immunosuppressants just before the relapse
 - Proportion of relapses of patients with Targeted biologic therapy just before the relapse
 - Proportion of relapses of patients using other treatments just before the relapse
 - Proportion of relapses for which Glucocorticoids (GCs) were used as medical care for the relapse
 - GCs dose used for relapse medical care (mg/day)
 - Proportion of relapses for which Immunosuppressants were used as medical care for the relapse
 - Proportion of relapses for which Targeted biologic were used as medical care for relapse
 - Proportion of relapses for which other GCA (HORTON) treatments were used as medical care for relapse.
 - Distribution of GCs dependence
 - Current dose at inclusion (mg/day)
 - Number of kinetics per patient since diagnosis
 - Time between first kinetic and diagnosis (months) ([APPENDIX](#))
 - Proportion of patients with at least one kinetic ongoing at inclusion
 - Mean time between 2 consecutive kinetics (months) ([APPENDIX](#))
 - Total cumulative GCs dose according to investigator (excluding IV bolus) since diagnosis (mg) ([APPENDIX](#))
 - The following information will be summarized by Kinetic:
 - Kinetic duration (months) ([APPENDIX](#))
 - Proportion of kinetics with IV initial administration (bolus) (Yes/No)
 - If yes, total number of days

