The percentages are calculated compared to filled data
STUDY : CHUGAI-ARTEMIS - Edition date: DDMMYY
Pgm : EFFICACYGCA.SAS

Listing 9 : Specification of other treatments used just before relapse (N= XX)

Patient ID	Number of relapse	Type of patient	Type of diagnosis	Physician who follows the patient	Specification of other treatments used just before relapse

STUDY : CHUGAI-ARTEMIS - Edition date: DDMMYY
Pgm : EFFICACYGCA.SAS

Listing 10 : Specification of other treatments used for the medical care of relapse (N= XX)

Patient ID	Number of relapse	Type of patient	Type of diagnosis	Physician who follows the patient	Specification of other treatments used as medical care for relapse

STUDY : CHUGAI-ARTEMIS - Edition date: DDMMYY
Pgm : EFFICACYGCA.SAS

Table 18 - Efficacy analysis – Clinical Form - Distribution of GCs dependance - Analysis population (N=XX)

Parameter	Statistics	Total (N=XX)
Current GCs dose at inclusion (mg/day)	Mean SD Median [Q1 ; Q3] [Min ; Max] Filled, n(%) Missing, n(%)	
Number of kinetics per patient since diagnosis	Mean SD Median [Q1 ; Q3] [Min ; Max] Filled, n(%) Missing, n(%)	
Time between first kinetic and diagnosis (months)	Mean SD Median [Q1 ; Q3] [Min ; Max] Filled, n(%) Missing, n(%)	
Patient with at least one kinetic ongoing at inclusion No Yes	n(%) n(%) Filled, n(%) Missing, n(%)	
Mean time between 2 consecutive kinetics (months)	Mean SD Median [Q1 ; Q3] [Min ; Max] Filled, n(%) Missing, n(%)	
Total cumulative GCs dose according to investigator (excluding IV bolus) since diagnosis (mg)	Mean SD Median [Q1 ; Q3] [Min ; Max] Filled, n(%) Missing, n(%)	

The percentages are calculated compared to filled data
STUDY : CHUGAI-ARTEMIS - Edition date: DDMMYY
Pgm : EFFICACY\GCA.SAS

Table 19 - Efficacy analysis – Clinical Form - Description of Corticotherapy (per kinetic) - Analysis population (N=XX)

Parameter	Statistics	Total (N=XX kinetics)
Kinetic duration (months)	Mean SD Median [Q1 ; Q3] [Min ; Max] Filled, n(%) Missing, n(%)	
Kinetic with IV initial administration (bolus) No Yes	n(%) n(%) Filled, n(%) Missing, n(%)	
If yes, Total number of days	Mean SD Median [Q1 ; Q3] [Min ; Max] Filled, n(%) Missing, n(%)	
IV bolus dose (mg)	Mean SD Median [Q1 ; Q3] [Min ; Max] Filled, n(%) Missing, n(%)	
Switch PO dose (mg/day)	Mean SD Median [Q1 ; Q3] [Min ; Max] Filled, n(%) Missing, n(%)	
Cumulative dose according to investigator (mg)	Mean SD Median [Q1 ; Q3] [Min ; Max] Filled, n(%) Missing, n(%)	

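### Two derived-variable formulas in the SAP conflict with the variables they define: the mean gap between glucocorticoid courses is divided by n instead of n-1, and BMI at diagnosis is computed from current weight

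*SAP*

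**What the plan says.** The formulas are in SAP section 8, in the derived-data appendix. Glucocorticoid courses are called kinetics there.

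- Item (8), the gap between courses: "Mean time between 2 consecutive kinetics (months) = [date of kinetic (i+1) – date of kinetic (i)]/Total number of kinetics per patient".
- Item (6), the same kind of quantity for relapses, has the divisor "Total number of relapses per patient-1".
- Item (7) defines a separate variable for the lead-in to the first course: "date of initiation of first kinetic – date of diagnosis".
- Item (10) shows that the appendix writes a summation sign where it wants one: "Total cumulative GCs dose (mg) = Σ Cumulative dose according to the investigator". Neither (6) nor (8) has one.
- Item (12), BMI, uses "Current weight (kg)/ [Height (cm)/100", with the height term squared. It is the only BMI formula in the SAP.

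The result of (8) is one row of Table 18. SAP 5.5.4.2 and Table 33 report BMI at diagnosis, and the factor lists for the relapse and disease-activity regressions in SAP 5.5.2 name BMI at diagnosis in classes. Protocol 5.3.1 collects weight at diagnosis and at the inclusion visit, and SAP 5.5.4.2 lists the two as separate variables. SAP 5.6, on changes from the protocol, mentions neither formula.

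**The concern.** **Item (8).** Three courses have two gaps, so an average gap has divisor two, not three. Item (7) already takes the time from diagnosis to the first course, which leaves no n-th gap to justify dividing by n. The shortfall depends on n. SAP 5.5.2 breaks clinical form down by type of patient, type of diagnosis and type of physician, so groups with different numbers of courses would be shrunk by different amounts. Part of an apparent difference between groups could come from the formula.

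**Item (12).** If current weight means weight at the inclusion visit, a variable labelled as a diagnosis measurement would carry any weight change since diagnosis. In the relapse model it would then be measured after the relapses it is meant to help explain.

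Program validation is not a safeguard. SAP 7.3 has outputs checked for consistency with the SAP, and a program that follows (8) or (12) to the letter passes that check.

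**Working it through.** The SAP gives no numerical result for these formulas, so there is no figure to reproduce. The check evaluates each formula as written.

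**Item (8).** Inputs: divisor n from (8) and divisor n-1 from (6). Assumption for illustration: every true gap is 12 months, so the gaps sum to 12(n-1).

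- (8) with the sum supplied: 12(n-1)/n
- (6) with the sum supplied: 12(n-1)/(n-1) = 12
- (8) read literally, one gap at a time: 12/n
- (6) read literally: 12/(n-1)

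| n | True mean | (8), with sum | Share of true | (8), literal | (6), with sum | (6), literal |
|---|---|---|---|---|---|---|
| 2 | 12 | 12/2 = 6 | 50% | 12/2 = 6 | 12/1 = 12 | 12/1 = 12 |
| 3 | 12 | 24/3 = 8 | 67% | 12/3 = 4 | 24/2 = 12 | 12/2 = 6 |
| 4 | 12 | 36/4 = 9 | 75% | 12/4 = 3 | 36/3 = 12 | 12/3 = 4 |

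At n = 2 there is only one gap, so (8) gives half the true value on either reading.

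Unequal gaps behave the same way. With starts at months 0, 6 and 24, the gaps are 6 and 18 and the true mean is 24/2 = 12. Item (8) with the sum gives 24/3 = 8. Read literally it gives two values, 6/3 = 2 and 18/3 = 6, for a row that needs one value per patient.

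At n = 1 there is no gap. A divisor of n-1 makes the quantity undefined, as it should be. A divisor of n gives 0/1 = 0 if an empty sum is programmed as zero, and that zero would enter the average.

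**Item (12).** First, the meaning of current weight. The term is not defined. Where the SAP applies the word to a patient's glucocorticoid dose it means the inclusion visit: "Current dose at inclusion (mg/day" in SAP 5.5.2, repeated in Table 18. Weight at inclusion is therefore the natural reading.

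Second, the scale. The error in BMI is (weight at inclusion − weight at diagnosis)/height². Assumed heights, chosen to span a plausible range:

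- 1.55 m: height² = 2.40, so 1 kg moves BMI by 1/2.40 = 0.42 kg/m²
- 1.75 m: height² = 3.06, so 1 kg moves BMI by 1/3.06 = 0.33 kg/m²

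Conversely, 2.4 to 3.1 kg moves BMI by one unit.

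The regressions use classes, so what matters there is crossing a cut point. Invented example: height 160 cm, 60 kg at diagnosis and 66 kg at inclusion. BMI is 60/2.56 = 23.4 against 66/2.56 = 25.8, and the patient moves from the 18.5-to-25 class to the 25-to-30 class.

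**The case against.** On (8), the fair objection is that the no-sum reading is implausible. Both formulas are titled as means and carry a running index, and n-1 in (6) makes sense only if the gaps are summed. That is right: the missing summation sign is a matter of notation, and (n-1)/n is the figure to rely on. The conflict with (6) remains on either reading. It is also true that the documents give no distribution of courses per patient, so the bias in the Table 18 row as a whole cannot be computed. Only the error for each patient is known.

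On (12), the reading of current weight is an inference. The SAP also uses the word relative to diagnosis, when it sets month windows for diagnostic tests (5.4) and for ESR and CRP (5.5.2). The dose rows add that they refer to inclusion, and (12) does not. A programmer might well follow the variable's label and use weight at diagnosis. In that case no result is wrong, but the formula still contradicts its label and needs the same edit. The BMI rows of Tables 22 and 26 carry no time point. They implement the factor lists in 5.5.2, which do, so they do not resolve the conflict.

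Finally, the effect of (12) on incident patients should be small, since diagnosis is at most 6 weeks before inclusion. This assumes that the diagnosis weight was taken at about the time of diagnosis; the SAP sets no window for it.

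**Conclusion.** Both formulas are wrong as written, and the point is minor.

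For (8) the error is certain. Every patient with two or more courses gets too short a gap: half the true value at two courses and, with the intended sum, (n-1)/n of it beyond that. One secondary descriptive row is affected.

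For (12) the conflict between formula and label is certain. Its effect on results depends on reading current weight as weight at inclusion, and its size is unknown because weight change since diagnosis is not given. It would reach the BMI rows of Table 33 and one candidate factor in each of two secondary regressions, mainly through prevalent patients.

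No primary endpoint uses either formula.

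**What to change.** Change three lines of the derived-data appendix:

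- (8): mean gap between courses = (start of last course − start of first course)/(number of courses − 1), missing when there is only one course.
- (6): mean gap between relapses = (date of last relapse − date of first relapse)/(number of relapses − 1), missing when there is only one relapse. The divisor is already right; this removes the doubt about the sum.
- (12): BMI at diagnosis = weight at diagnosis (kg)/[height at diagnosis (cm)/100]².

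Adding the time point to the BMI rows of Tables 22 and 26 would be a useful tidy-up.

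The cost is a text edit and matching program lines. Course dates, relapse dates, and weight and height at diagnosis are already among the SAP's variables, so nothing new has to be collected.
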